- i. With the exception of the urine dipstick and baseline pregnancy testing, a central laboratory will be used. Any baseline results received while participants are On-treatment that are exclusionary will be assessed by the medical monitor. The medical monitor will contact the investigator and advise on appropriate action with the study intervention.
- j. Measure temperature, blood pressure, respiratory rate, and pulse rate. See Section 8.3.2 for additional details.
- k. For women of childbearing potential, a negative high sensitivity urine pregnancy test is sufficient for eligibility. A pregnancy test will be performed predose and just before taking the fifth dose. The pregnancy test before the fifth dose will be done at home using a test kit supplied at Baseline, with the result confirmed at Visit 4.
- l. VRCC will confirm the doses of study intervention taken the previous day and results of at home pregnancy tests. AEs will not directly be asked about by VRCC, and VRCC will direct any AEs, SAEs, or concomitant medications reported during telephone visits directly to the study site; the study physician or otherwise appropriate medically trained staff from the study site will follow-up with the participant.
- m. The study physician or otherwise appropriate medically trained staff from the study site will perform a safety telephone call at Visit 6 (CCI [REDACTED]), and at Visit 7 (± 3 days). The study physician or otherwise appropriate medically trained staff from the study site will follow-up with participants who report an AE, SAE, or use of a concomitant medication to VRCC.
- n. CCI
[REDACTED]
- o. Participants must have taken 2 doses of study intervention before the Visit 2 CSS telephone assessment. This will be confirmed during the Visit 2 telephone call. For any participants who have not received 2 doses of study intervention, a second telephone call will be scheduled to perform the CSS after the second dose has been taken.
- p. The CCI CCI will be administered to participants via a telephone interview performed by VRCC. These assessments will be performed by the same interviewer who determines the CSS. See Section 8.2.2 for additional information.

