 - Participants unable to take 2 doses as prescribed before the CSS assessment at 24 hours (± 4 hours) (Principal Stratum Strategy). Interest lies in the group of participants who complied with the 2 doses as prescribed before the CSS assessment at 24 hours (± 4 hours).
 - A participant using other systemic antimicrobials (for uUTI or other infections) on or before the CSS assessment at 24 hours (± 4 hours) (Composite Strategy). This ICE is incorporated into the definition of the endpoint.
- The population-level summary to be estimated is percentage of participants who achieve clinical symptom improvement and its 95% Exact Binomial CI.

RATIONALE FOR PRIMARY ESTIMANDS:

- Interest lies in evaluating study intervention benefit through a decrease in CSS total score in participants who achieve 100% compliance to study intervention before the CSS assessment at 24 hours (± 4 hours).
- Participants who take other antimicrobials for uUTI indicate lack of treatment benefit and will not be able to achieve symptom improvement (i.e., treatment failures). Participants who take other antimicrobials for other infections might confound the outcome by improving the symptoms. Therefore, such participants are also set to treatment failures.

SUPPLEMENTARY ESTIMAND FOR PRIMARY ENDPOINT:

A supplementary estimand will be considered if **CCI** participants are not able to comply with the 2 doses as prescribed before the CSS assessment at 24 hours (± 4 hours).

The additional clinical question of interest is to assess symptom improvement without the need for other systemic antimicrobials in participants at 24 hours (± 4 hours) after the initial dose of gepotidacin.

The supplementary estimand is described by the following attributes:

- The population is female participants aged ≥ 12 years with suspected uUTI.
- The endpoint is achieving clinical symptom improvement, defined as a decrease from Baseline in CSS total score of at least 1 point at 24 hours (± 4 hours), without the need for other systemic antimicrobials.
- The treatment condition is gepotidacin 1500 mg BID.
- The ICEs and estimand strategies are as follows:
 - Participants unable to take 2 doses as prescribed before the CSS assessment at 24 hours (± 4 hours) (Treatment Policy Strategy). Interest lies in the treatment effect regardless of compliance with the study intervention.

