6.1. Study intervention administered

All doses of study intervention are to be taken after food consumption and with water. Participants will receive oral study intervention (gepotidacin [2 × 750 mg tablets]) BID (approximately every 12 hours) for 5 days. Doses are to be taken approximately 12 hours apart, but the allowable window is 6 to 14 hours. There must be at least a 6-hour minimum window between doses. The first oral dose will be administered at the study site at Baseline; participants will self-administer subsequent doses as outpatients thereafter.

Each treatment day will be assessed over a 24-hour period, starting with the first dose of study intervention received for an individual participant. For example, participants who only receive 1 dose of study intervention on their first calendar day in the study due to a late afternoon/evening Visit 1 will take the second dose on the following calendar day, which will complete Day 1. This pattern will continue until all 10 doses are received; thus, the tenth/last dose will be taken prior to Visit 5 (may be 5 or 6 calendar days, depending on when the first dose is taken).

Gepotidacin tablets (750 mg) are not to be broken and must be swallowed whole. The dosage schedule must always encourage study intervention to be taken as close to 12 hours apart as possible.

Table 3 Study intervention administered

Intervention Name	Gepotidacin
Intervention Description	Administer BID (every 12 hours) for 5 days: 1500 mg as 2 × 750 mg tablets for a 3000 mg total daily dose Each dose is to be taken after food consumption and with water
Type	Drug
Dose Formulation	Tablets containing gepotidacin and inactive formulation excipients
Unit Dose Strength	750 mg tablets
Dosage Level	1500 mg BID
Route of Administration	Oral
Use	Investigational
Sourcing	Provided centrally by GSK ^{CCI}
Packaging and Labeling	Gepotidacin tablets will be provided in bottles with required labeling
Manufacturer	^{CCI} [REDACTED]

The supply and shipping of the study intervention will be supported by Xpress.

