7. DISCONTINUATION OF STUDY INTERVENTION AND PARTICIPANT DISCONTINUATION/WITHDRAWAL

7.1. Discontinuation of study intervention

Participants may voluntarily discontinue study intervention at any time. The investigator may also, at his or her discretion, discontinue the participant from study intervention at any time and initiate appropriate alternative therapy.

The primary reason for premature discontinuation of study intervention will be documented in the eCRF based on the list below:

- Adverse event
- Protocol deviation
- Termination of the study by GSK
- Lost to follow-up
- Investigator discretion
- Lack of efficacy
- Pregnancy
- Study site terminated by sponsor
- Withdrawal by participant
- Participant reached protocol-defined stopping criteria

- Other (specify)
- Death

Participants who discontinue study intervention for the reasons above will not be considered withdrawn from the study and should participate in all subsequent study visits (see Section 1.3).

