- Clinical laboratory tests will be conducted, vital signs will be measured, and a 12-lead ECG and physical examination will be performed.
- Following completion of all pretreatment assessments, participants who meet the inclusion and exclusion eligibility criteria will receive oral gepotidacin 1500 mg BID for 5 days. The first dose of study intervention will be administered at the study site under supervision. After dose administration, Visit 1 posttreatment assessments will be performed, as shown in the SoA (Section 1.3). Subsequent to administration of the first dose at the study site, participants will self-administer doses as outpatients, beginning with the second dose. (Note: Each dose is to be taken after food consumption and with water.)
- AEs, SAEs, and concomitant medication use will be recorded, and any AEs or clinically significant changes will be followed accordingly.
- Visit 2 will be scheduled before the participant leaves the study site at Visit 1 (as indicated in Section 1.3).

- **Visit 2 (On-treatment): telephone visit 24±4 h after the first dose**
 - Participants must have taken a total of 2 doses of gepotidacin before the Visit 2 assessment of CSS. This will be confirmed during the Visit 2 telephone call.
 - Clinical symptoms of uUTI will be recorded first based on a participant telephone interview performed by VRCC, who will determine the individual uUTI CSS.
 - The **CCI** will be completed by VRCC last. The same scorer will be used at all assessment time points for each participant, on all occasions, whenever possible.
 - Study intervention compliance will be recorded.
 - Participants will self-administer gepotidacin as an outpatient every 12 hours. Gepotidacin is to be taken after food consumption and with water to assist with tolerability.
 - AEs, SAEs, and concomitant medication use will be recorded, and any AEs or clinically significant changes reported to VRCC during the visit will be followed-up with the study site accordingly.
 - Remind participants of the at home pregnancy test that will be performed before the fifth dose of study intervention.
 - Visit 3 will be scheduled.
- **Visit 3 (On-treatment): telephone visit 48±4 h after the first dose**
 - The CSS assessment will be completed first based on a participant telephone interview performed by VRCC.
 - **CCI**
 - Study intervention compliance will be recorded.

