#### **4.2.4. Supplementary estimand for primary endpoint and analysis**

A supplementary estimand analysis for primary endpoint will be conducted if **cci** of participants in the ITT analysis set are unable to comply with the 2 doses of gepotidacacin before 24 hours ( $\pm$ 4 hours). Supplementary estimand analysis will be performed using ITT analysis set. Thereby including those participants who were unable to adhere to the 2 doses of treatment as prescribed before 24 hours ( $\pm$ 4 hours) and were excluded from the CE24 set. Participants who are unable to complete the CSS assessment at 24 hours ( $\pm$ 4 hours) will be considered treatment failures and included in the analysis as not improvers. Percentage of participants who achieve clinical symptom improvement along with the 95% exact Binomial CI will be produced in supplementary estimand analysis for primary efficacy endpoint.

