**Table 3 Analysis Assessment Window for Post-Baseline**

Timepoints Analysis Set / Domain	Protocol Visit Window/ Extended Visit Window	Target	Analysis Timepoint Window	
			Beginning Timepoint	Ending Timepoint
Efficacy (Primary, Secondary and Exploratory)	24 hours $\pm$ 4 hours	24 hours	$\geq$ 20 hours	$\leq$ 28 hours
	24 hours $\pm$ 12 hours		$>$ 12 hours	$\leq$ 36 hours
	48 hours $\pm$ 4 hours	48 hours	$\geq$ 44 hours	$\leq$ 52 hours
	48 hours $\pm$ 12 hours		$>$ 36 hours	$\leq$ 60 hours
	72 hours $\pm$ 4 hours	72 hours	$\geq$ 68 hours	$<$ 76 hours
	72 hours $\pm$ 12 hours		$>$ 60 hours	$\leq$ 84 hours
	96 hours $\pm$ 4 hours	96 hours	$\geq$ 92 hours	$\leq$ 100 hours
	96 hours $\pm$ 12 hours		$>$ 84 hours	$\leq$ 108 hours
CCI				

If multiple records exist within the same analysis timepoint window, then the record occurring closest to the target hours/day will be utilized in all analyses and analysis set determinations. If multiple records are equally close to the target hours/day, then the later record will be utilized. If multiple records occur on the same hours/day and time is not collected, then the record with the larger Study Data Tabulation Model (SDTM) record sequence number will be utilized in all analyses. All protocol assessments (including unscheduled and early termination timepoints) will be presented in participant listings. Both the nominal and analysis timepoint will be presented in listings.

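### The 24 h CSS is withheld until dose 2 is taken, so some women whom the treatment-policy ITT analysis is meant to include count as failures without being measured

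*Protocol*

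**What the plan says.** Protocol Section 8 (Visit 2) sets the condition: "Participants must have taken a total of 2 doses of gepotidacin before the Visit 2 assessment of CSS". Footnote o to the schedule of activities (Protocol 1.3) says what happens otherwise: "a second telephone call will be scheduled to perform the CSS after the second dose has been taken". Neither place gives a latest time for that second call, or a CSS for someone who never takes dose 2. Protocol 7.1 nevertheless says that participants who stop treatment "will not be considered withdrawn from the study and should participate in all subsequent study visits".

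The supplementary estimand for the primary endpoint (Protocol Section 3) treats failure to take two doses by treatment policy: "Interest lies in the treatment effect regardless of compliance with the study intervention". SAP 4.2.4 runs it on the ITT set and gives the reason: "Thereby including those participants who were unable to adhere to the 2 doses of treatment as prescribed before 24 hours". That section counts a CSS not completed at 24 h as failure. SAP Table 1 puts a CSS outside the visit window under *Unable to determine*, and SAP 4.2.1 counts that outcome as not improved. SAP 4.3.1.4 does the same for 24 h resolution on ITT.

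On record selection, SAP 6.3.6 has one rule for several records in a window: "the record occurring closest to the target hours/day will be utilized in all analyses and analysis set determinations". On dosing, Protocol 6.1 says: "Doses are to be taken approximately 12 hours apart, but the allowable window is 6 to 14 hours".

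**The concern.** A treatment-policy strategy needs the outcome to be measured whether or not the intercurrent event occurs. Here the intercurrent event (no second dose) decides whether the outcome is measured at all, and non-measurement is then coded as failure. For the women concerned, the estimate says nothing about how their symptoms went. It counts them as failures because they did not take dose 2, which is a composite strategy under another name.

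What is at stake is the supplementary ITT analysis of 24 h improvement and of 24 h resolution, the check on what restricting the primary analysis to two-dose takers does to the result. The descriptive ITT displays of CSS at 24 h (SAP 4.2.2) and the ITT shift tables (SAP 4.3.1.2) lose the same scores, and they are produced whatever the level of non-compliance.

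**Working it through.** **Which women lose their score.** Following the rules through for each dose 2 pattern:

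1. Dose 2 late, but before a call within 20 to 28 h: CSS done in window, so she is scored.
2. No dose 2 at the call, then dose 2 and the second call both by 28 h: she is scored.
3. No dose 2 at the call, and the deferred CSS falls after 28 h: out of window, *Unable to determine*, failure. If dose 2 itself came by 28 h and a simple dose count satisfies the CE24 definition in SAP Section 3, she is also a failure in CE24.
4. Dose 2 never taken: no Visit 2 CSS is provided for, so failure.

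Only patterns 3 and 4 are affected. Within them, a woman who took another systemic antimicrobial by the assessment fails under the composite component anyway, and an unscheduled or early-withdrawal CSS that happens to fall in the window would give a score.

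**Does the primary estimand need the condition at data collection?** CE24 applies the two-dose condition at analysis. The Visit 2 window opens at 24 − 4 = 20 h, and the longest interval in Protocol 6.1 is 14 h. A woman without dose 2 at an in-window call is therefore already beyond that interval. If *as prescribed* enforces the interval, she is outside CE24 and deferral gains nothing for the primary analysis. If it means a dose count, she can enter CE24 with a CSS taken soon after dose 2. The visible text does not say which.

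**Does imputation repair it?** SAP 4.2.4.1 imputes on ITT using Steps 1 and 2 of SAP 4.2.3, under missing at random. With almost no observed 24 h scores among women without dose 2, the model has to borrow from women who took it.

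**The plan's own figure.** Protocol 1.1 gives about 90 enrolled, at least 82 evaluable, 74% response and a 95% CI half-width of about 10% or less. Using exact limits Beta(0.025; x, n−x+1) and Beta(0.975; x+1, n−x), with n = 82 and x = 0.74 × 82 = 60.68, the interval is 63.1% to 83.1%, half-width 9.97%. The figure reproduces and is not in dispute.

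**Illustration.** Assume 61 responders among 82 in CE24, and that all 90 − 82 = 8 others lack an in-window score. Let r be the number of those 8 who would have been responders if measured. The ITT rate with measurement is (61 + r)/90. The rules as written set r = 0.

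| Case | r | ITT rate | Lost to the rule |
|---|---|---|---|
| As written | 0 | 61/90 = 67.8% (exact 95% CI 57.1 to 77.2) | – |
| Measured, 50% respond | 4 | 65/90 = 72.2% | 4.4 points |
| Measured, same rate as CE24 | 8 × 61/82 = 5.95 | 66.95/90 = 74.4% | 6.6 points |
| Measured, all respond | 8 | 69/90 = 76.7% | 8.9 points |

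For comparison, CE24 is 61/82 = 74.4% (63.6 to 83.4). With k unscored women and equal response at 74%, the loss is 0.74 × k/90: 1.6 points for k = 2, 4.1 for k = 5 and 6.6 for k = 8. If half of the 8 were scored after all (k = 4), it is 3.3 points.

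**The case against.** The strongest reply is that the reach is limited, and much of that stands.

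- The supplementary estimands run only above a non-compliance threshold that is redacted. The 8/90 = 8.9% in the illustration may fall below it, so 67.8% might never be reported. But the ITT displays are unconditional, and scores not collected cannot be recovered once the threshold is met.
- A reader might infer that most of the women ITT adds to CE24 have no score. The documents do not support that: they give no count of non-adherers, and *as prescribed* has no visible operational definition. If it enforces the 6 to 14 h interval, women who took dose 2 late but before the call are outside CE24 and still scored.
- SAP Table 3 also lists a 24 ± 12 h window, which could admit some late scores. The visible text does not say where it applies, and the estimand and Table 1 use ± 4 h.
- A reader might also take 8.9 points as the expected bias. It is an extreme bound, requiring all 8 to have missed dose 2 and every one of them to have improved. Nothing visible says the margin of 8 consists of missed second doses.
- Deferral has a purpose. After a call at, say, 20 to 24 h, dose 2 and the second call can still fall by 28 h, and on a dose-count reading this keeps a participant evaluable for the primary analysis. That justifies keeping the second call, but not omitting the CSS at the first.

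**Conclusion.** The point holds for a defined group: women without dose 2 at the Visit 2 call who never take it, or whose deferred CSS falls after 28 h. Unless another visit supplies an in-window CSS, they are failures by rule in the supplementary ITT analyses of 24 h improvement and resolution, and the declared treatment-policy strategy does not describe what is estimated for them. The planned imputation does not replace the missing information.

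The share affected is unknown. The 6.6 points rests on three assumptions: all 8 lack an in-window score, they would have responded at the CE24 rate, and the ± 4 h window governs. The documents do not support a claim that the primary result is materially biased. The trial has no hypothesis test, and the primary analysis does not depend on this estimand. The change is worth making because the call already takes place and the lost scores cannot be rebuilt later.

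**What to change.** **Protocol (footnote o and Section 8, Visit 2).** Perform the CSS at the first Visit 2 call within 20 to 28 h regardless of doses taken, and record the number and times of doses. Keep the existing second call for a CSS after dose 2.

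**SAP 6.3.6.** Replace the single closest-record rule for this timepoint. Use the in-window CSS after dose 2 for CE24, and the in-window CSS closest to 24 h regardless of doses for the ITT estimand and ITT displays. State where the 24 ± 12 h window applies.

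**Reconcile.** Footnotes o and q of the schedule of activities, Protocol 6.1 and the CE24 definition in SAP Section 3 must agree on which call completes Visit 2 (footnote q ties the third dose to completion of the Visit 2 assessments) and on what *as prescribed* means for CE24.

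**If the protocol is not changed.** Relabel the supplementary strategy for a missed dose 2 as composite (failure), so that the estimand matches the estimate. This needs no new data, but gives up the treatment-policy question.

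**Cost.** A protocol amendment with its approvals, and SAP wording. A few women answer the four CSS items twice, and one woman may be a responder in one analysis and a failure in the other, which the report should explain. No extra call is needed.

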2. INTRODUCTION

Gepotidacin (GSK21409144) is a novel, bactericidal, first-in-class triazaacenaphthylene antibiotic that inhibits bacterial DNA replication by a distinct mechanism of action and binding site [Bax, 2010; Gibson, 2019] and provides well-balanced inhibition of 2 different type II topoisomerase enzymes [Oviatt, 2022]. This provides activity against most strains of target uUTI uropathogens, such as *Escherichia coli* and *Staphylococcus saprophyticus*, including isolates resistant to current antibiotics [Biedenbach, 2016; Mushtaq, 2019]. Due to well-balanced binding at both enzymes, mutations in both enzymes are needed to significantly affect gepotidacin susceptibility [Oviatt, 2022].

uUTIs, also referred to as acute cystitis, are defined as UTIs in nonpregnant female patients with no known urological abnormalities or complicating comorbidities and not accompanied by signs or symptoms suggesting systemic (i.e., not localized to the bladder) infection, such as fever or costovertebral angle pain [Gupta, 2011; DHHS, 2019]. Common symptoms of uUTIs are pain on urination (dysuria), frequent urination (frequency), sudden onset of the need to urinate (urgency), pain in the lower abdomen (suprapubic pain), inability to start the urine stream (hesitancy), and cloudy urine or blood in the urine (hematuria). In addition to the physical symptoms, uUTIs have been shown to affect a patient's quality of life and their emotional and mental health [Grigoryan, 2022].

2.1. Study rationale

The patient burden of uUTI is significant, with each episode of uUTI associated with approximately 6 symptomatic days, 2 to 3 days of restricted activity, and an unknown amount of time lost from work. Most of the symptoms experienced by patients were rated as moderate to severe in intensity and some of them were the most common associated with impairment of daily living. There is a need to better assess the burden of UTIs in women because few data are available that describe patient-reported outcomes regarding time to improvement and resolution of uUTI symptoms. Feedback from patients and providers states that patients want to feel better after the first dose of treatment and it has been shown that rapid reversal of the overall severity of uUTI symptoms allows the patient to resume normal work/social activities [Klimberg, 2005].

The Phase 3 gepotidacin studies conducted in uUTI (Section 2.2) were conducted based on the need to identify new and effective oral antibiotic treatment options for uUTIs, as such therapies are becoming limited due to the increase in MDR pathogens and ESBL-producing Enterobacteriales pathogens, which are impacting the efficacy of the currently available oral antibacterial treatment options (see Section 2.2).

More recently, two Phase 3 clinical studies (Study 204989 and Study 212390) that assessed gepotidacin (1500 mg BID for 5 days) compared with nitrofurantoin (100 mg BID for 5 days) in uUTI showed gepotidacin was non-inferior in the primary therapeutic response evaluated at a preplanned interim analysis in both studies and superior to nitrofurantoin in study 212390. Full data analyses and reporting activities are complete [Study 204989, (NCT04020341); Study 212390, (NCT04187144); Hall, 2023] for both Phase 3 trials.

The Phase 3 primary endpoint in the studies was a composite of both clinical and microbiological success captured at the Test of Cure Visit, 10 to 13 days after randomization. **CCI**

CCI

CCI

The purpose of this Phase 3b study for gepotidacin in female participants with uUTI is to evaluate clinical symptom improvement on each day during the 5-day treatment period, specifically including the 24-hour time point. The microbiological components of uUTIs were fully assessed in Study 204989 and Study 212390. These additional data are expected to align with current clinical practice and to inform practitioners on the potential use of gepotidacin in uUTIs.

